5.1 Imputation rules

5.1.1 Study drug

Partial dose date is not allowed in data collection.

5.1.2 AE date imputation

Impute AE end date:

1. If the AE end date ‘month’ is missing, the imputed end date should be set to the earliest of the (last visit date, 31DECYYYY, date of death).
2. If the AE end date ‘day’ is missing, the imputed end date should be set to the earliest of the (last visit date, last day of the month, date of death).
3. If AE ‘year’ is missing or AE is ongoing, the end date will not be imputed.

Impute AE start date:

Before imputing AE start date, find the AE start reference date as below.

- If the (imputed) AE end date is complete and the (imputed) AE end date < treatment start date then AE start reference date = min (informed consent date, earliest visit date)
- Else AE start reference date = treatment start date

1. If the AE start date 'year' value is missing, the date uncertainty is too high to impute a rational date. Therefore, if the AE year value is missing, the imputed AE start date is set to NULL.
2. If the AE start date 'year' value is less than the treatment start date year value, the AE started before treatment. Therefore:
 - a. If AE 'month' is missing, the imputed AE start date is set to the mid-year point (01JulYYYY).
 - b. Else if AE 'month' is not missing, the imputed AE start date is set to the mid-month point (15MONYYYY).
3. If the AE start date year value is greater than the treatment start date year value, the AE started after treatment. Therefore:
 - a. If the AE month is missing, the imputed AE start date is set to the year start point (01JanYYYY).
 - b. Else if the AE month is not missing, the imputed AE start date is set to the later of (month start point (01MONYYYY), AE start reference date + 1 day).
4. If the AE start date year value is equal to the treatment start date year value:
 - a. And the AE month is missing the imputed AE start date is set to the AE reference start date + 1 day.
 - b. Else if the AE month is less than the treatment start month, the imputed AE start date is set to the mid-month point (15MONYYYY).
 - c. Else if the AE month is equal to the treatment start date month or greater than the treatment start date month, the imputed AE start date is set to the later of (month start point (01MONYYYY), AE start reference date + 1 day).

If complete (imputed) AE end date is available and the imputed AE start date is greater than the (imputed) AE end date, then imputed AE start date should be set to the (imputed) AE end date.

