Final efficacy and safety analyses will be conducted on the entire study period (all periods of double blind, open label and safety follow up).

[figure not shown]
The treatment groups and the data to be used for final analysis are shown in [Table 2-2](#).

Please note: efficacy analysis for “Placebo – LOU064 25mg “treatment group will be provided for all participants initially randomized to placebo regardless of entering the open-label treatment. The efficacy data from baseline to Week 24 will be assessed under placebo. The data after the first dose of LOU064 will be assessed under LOU064 25mg treatment, but separated from the LOU064 25mg treatment group (participants initially randomized to LOU064). Safety analysis for “Transitioned to LOU064” group will be conducted using safety data after switching to LOU064 25 mg treatment.

Table 2-2 Treatment groups for final analyses

Endpoint	Period	Treatment group	Details
Efficacy	Entire study (DB period + OL period)	LOU064 25mg	Participants initially randomized to LOU064 Efficacy from baseline to Week 52
		Placebo - LOU064 25mg	Participants initially randomized to placebo regardless of entering into OL period, i.e. including participants who discontinued during DB period and not entered into OL period, participants who entered into OL period and switched to LOU064. Efficacy from baseline up to Week 52. Note: the data from baseline to Week 24 is under placebo, the data after the first dose of LOU064 is under LOU064 25mg
Safety	Entire study (DB period + OL period + FW period)	LOU064 25mg	Participants initially randomized to LOU064 Safety from baseline up to the end of study
		Placebo	Participants initially randomized to placebo Safety from baseline up to Week 24
	Transitioned to LOU064 25mg	Participants initially randomized to placebo and switched to LOU064 25mg Safety after switching to LOU064 up to the end of study	

DB: double-blind, OL: open-label, FW: follow-up

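### SAP 5.1.2 ignores the first open-label dose when it imputes partial AE start dates, so in placebo switchers an ambiguous event is counted under Placebo and not under Transitioned to LOU064

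*SAP*

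**What the plan says.** SAP 5.1.2 first sets a reference date. An AE that ended before treatment takes an early reference (consent or first visit). For all others: "Else AE start reference date = treatment start date". The section does not define treatment start date.

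The branches for a partial start date are then:

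- Year missing: no imputation, because "the date uncertainty is too high to impute a rational date" (rule 1).
- Year or month before treatment start: mid-year, or "the imputed AE start date is set to the mid-month point (15MONYYYY" (rules 2 and 4b).
- Later year, month missing: "If the AE month is missing, the imputed AE start date is set to the year start point (01JanYYYY") (rule 3a).
- Later year, or the same year in or after the starting month, with only the day missing: "set to the later of (month start point (01MONYYYY), AE start reference date + 1 day") (rules 3b and 4c).
- Same year, month missing: "And the AE month is missing the imputed AE start date is set to the AE reference start date + 1 day" (rule 4a).

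If the result is later than the AE end date, "then imputed AE start date should be set to the (imputed) AE end date". That cap can only move a date earlier.

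The first open-label dose appears nowhere in these rules, yet the safety groups depend on it. SAP 2.1.1.1 states that the Transitioned analysis is "conducted using safety data after switching to LOU064 25 mg treatment". SAP 2.1.1.4 ends the double-blind period no later than the day before the first open-label dose and starts the Transitioned on-treatment period on that dose. SAP 2.7.1 counts treatment-emergent events by on-treatment period.

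**The concern.** For an on-treatment event the rules choose the earliest date that fits the known parts. If the missing part leaves open whether the event began before or after the switch, the earliest date is on the double-blind side. In a placebo-randomised participant, an event that began on open-label remibrutinib is then reported under Placebo.

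The entire-study tables, which are the only treatment-emergent AE tables planned for the final analysis (SAP Table 2-13), have three columns. The LOU064 column covers both periods and keeps its events. Transitioned can lose events and Placebo can gain them. Placebo exposure still ends at the last double-blind dose (SAP Tables 2-10 and 2-11), so exposure-adjusted rates for Placebo would gain events without gaining the open-label time in which they arose. For infections, bleeding and cytopenias, SAP 2.7.1.1 also reports onset time and double-blind time windows. Rule 4a can place an event from after Week 24 on Day 2, in the first of those windows.

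The SAP already guards against this for visit data: SAP 2.1.1.5 does not let assessments made on LOU064 after the switch be remapped to double-blind visits. AE dates have no such guard, although SAP 5.1.1 requires complete dose dates, so the date needed is always known.

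**Working it through.** The plan gives no figure on this point to reproduce. I coded SAP 5.1.2 as written and enumerated it.

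**Inputs.** Switch at Week 24, Day 169 (Protocol 6.1.3 and Table 8-1). Assumed: first dose equally likely on each of 365 days of one calendar year; AE onset equally likely on each study day; treatment start date read as the first double-blind dose, as the safety Day 1 definition in SAP 2.1.1.3 supports.

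**Denominators.** Double-blind onsets: 365 × 168 = 61,320. Open-label onsets, Days 169–365: 365 × 197 = 71,905. To Day 394: 365 × 226 = 82,490.

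**Open-label onsets imputed before the first open-label dose**

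| Missing | To Day 365 | To Day 394 |
|---|---|---|
| Day only | 5,373 / 71,905 = 7.5% | 5,373 / 82,490 = 6.5% |
| Day and month | 52,402 / 71,905 = 72.9% | 56,839 / 82,490 = 68.9% |

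Double-blind onsets imputed to open label: 0 of 61,320 in every run. Of the 56,839 month-missing shifts, 37,336 come from rule 3a (1 January) and 19,503 from rule 4a.

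**Example.** First dose 10 January 2022, open label from 27 June 2022.

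- True onset 5 September, month missing: imputed 11 January, under placebo.
- True onset 5 September, day missing: imputed 1 September, correctly open label.
- True onset 29 June, day missing: imputed 1 June, under placebo.

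**Other reading of the anchor.** If treatment start date meant the first open-label dose for the Transitioned group, the direction would reverse. No open-label onset moves to placebo. With the end date unknown, 5,373 / 61,320 = 8.8% (day missing) or 47,124 / 61,320 = 76.8% (month missing) of placebo-period onsets move to open label. With an end date 3 days after onset these fall to 1.7% and 1.8%.

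**Wrong period in either direction, current rule against the proposed rule** (onsets to Day 365, N = 61,320 + 71,905 = 133,225)

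| Missing | AE end date | Current | Proposed |
|---|---|---|---|
| Day | unknown | 5,373 = 4.0% | 5,373 = 4.0% |
| Day | onset + 3 days | 5,373 = 4.0% | 1,023 = 0.8% |
| Day | onset + 14 days | 5,373 = 4.0% | 3,850 = 2.9% |
| Month | unknown | 52,402 = 39.3% | 47,124 = 35.4% |
| Month | onset + 3 days | 52,402 = 39.3% | 1,089 = 0.8% |
| Month | onset + 14 days | 52,402 = 39.3% | 5,005 = 3.8% |

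The current column does not change with the end date, because the rule never uses it to place an event relative to the switch.

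The proposed column needs the open-label dose to act as a floor in every on-treatment branch. Rule 3a does not use the reference date, so changing the reference alone leaves its 32,899 errors (onsets to Day 365). Month missing, the total error would then be (32,899 + 591) / 133,225 = 25.1% with an end date 3 days after onset, and (32,899 + 33,096) / 133,225 = 49.5% with the end date unknown.

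**Number of events, illustration only.** Assume 200 open-label AEs in the Transitioned group, 1–3% with partial start dates, and one in ten of those lacking the month. The chance that a partial date is misplaced is 0.9 × 0.075 + 0.1 × 0.729 = 0.140. This gives 2 × 0.140 = 0.3 to 6 × 0.140 = 0.8 events.

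**The case against.** The rule has a sound purpose. Placing a date that straddles the first dose just after it makes the event treatment-emergent, which is cautious at the boundary between pre-treatment and on-treatment. Partial dates should also be rare: AEs are sought at every visit (Protocol 10.1.1), missing values are queried (Protocol 11.2) and SAEs are reported within 24 hours (Protocol 10.1.3). Both arguments stand. They limit the size of the problem but do not address the second boundary, at the switch.

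Three stronger readings are tempting and should not be drawn.

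- A reader might infer that partial dates always go to the first double-blind dose. They do not. Only rule 4a and the floor in rules 3b and 4c use that date, and a day-missing date in any month after the switch month is classified correctly.
- A reader might infer that the randomised double-blind comparison is tilted towards remibrutinib. The rule takes no account of arm. Remibrutinib-randomised participants also enter open label, and their ambiguous events move into the double-blind remibrutinib column in the same way.
- A reader might take the direction as fixed by the text. It depends on an undefined term. Tables 2-10 and 2-11 give the first open-label dose as the first dose of study treatment for the Transitioned group, and that reading reverses the direction. The safety Day 1 definition favours the double-blind dose. So does rule 2, which treats earlier events as before treatment and would misdescribe events on placebo if the anchor were the open-label dose.

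**Conclusion.** The point holds in limited form. With treatment start date read as the first double-blind dose, SAP 5.1.2 puts every on-treatment partial date that spans the switch into the double-blind period. In placebo-randomised participants (one third of those randomised) this can move open-label remibrutinib events to Placebo and never the reverse: about 7% of open-label AEs with only the day missing and about 70% with the month missing. The one-sided effect is confined to the Placebo and Transitioned columns of the entire-study tables, a non-randomised contrast.

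The percentages rest on the assumed enrolment calendar and uniform onset, and apply only to AEs with partial dates. The likely number of events is very small, so this is a minor improvement that would matter only for a rare event of special interest. The undefined term needs correcting in any case, because the direction of the error depends on it.

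**What to change.** In SAP 5.1.2:

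1. Define treatment start date as the first double-blind dose.
2. Add one rule, identical in both arms. If the known parts of the start date, and the AE end date where available, are compatible with onset on or after the first open-label dose, use that dose as the reference. State that the imputed start may not precede it in any on-treatment branch, including the 1 January branch, subject to the existing cap at the AE end date. Otherwise keep the current rule.
3. Footnote the safety tables with the number of AEs whose period rests on an imputed date, and give the count under the opposite assignment.

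The rule should not be limited to placebo switchers. That would handle identical dates differently by arm in the double-blind tables, which are the randomised safety comparison.

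The cost is a short addition to the SAP and a few lines of code. The downside is that some true double-blind events with long or unknown duration will be counted under open label: with the end date unknown, 8.8% (day missing) or 76.8% (month missing) of double-blind onsets that have partial dates. For placebo switchers that is the conservative direction. In the double-blind tables both arms are treated alike, and the opposite-assignment count shows whether it matters.

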5.1.3 Concomitant medication date imputation**Impute concomitant medication (CM) end date:**

1. If CM end day is missing and CM month/year are non-missing then impute CM day as the minimum of treatment end date and the last day of the month.
2. If CM end day/month are missing and CM year is non-missing then impute CM day as the minimum of treatment end date and the end of the year (31DECYYYY).
3. If imputed CM end date is less than the CM start date, use the CM start date as the imputed CM end date.

Impute CM start date:

1. If the CM start date year value is missing, the imputed CM start date is set to one day prior to treatment start date.
2. If the CM start date year value is less than the treatment start date year value, the CM started before treatment. Therefore:
 - a. If the CM month is missing, the imputed CM start date is set to the mid-year point (01JulYYYY).
 - b. Else if the CM month is not missing, the imputed CM start date is set to the mid-month point (15MONYYYY).
3. If the CM start date year value is greater than the treatment start date year value, the CM started after treatment. Therefore:
 - a. If the CM month is missing, the imputed CM start date is set to the year start point (01JanYYYY).
 - b. Else if the CM month is not missing, the imputed CM start date is set to the month start point (01MONYYYY).
4. If the CM start date year value is equal to the treatment start date year value:
 - a. And the CM month is missing or the CM month is equal to the treatment start date month, then the imputed CM start date is set to one day prior treatment start date.
 - b. Else if the CM month is less than the treatment start date month, the imputed CM start date is set to the mid-month point (15MONYYYY).
 - c. Else if the CM month is greater than the treatment start date month, the imputed CM start date is set to the month start point (01MONYYYY).

If complete (imputed) CM end date is available and the imputed CM start date is greater than the (imputed) CM end date, then imputed CM start date should be set to the (imputed) CM end date.

5.1.4 Concomitant therapies

Please see [Section 5.1.3](#).

5.1.5 Other imputations

First diagnosis date imputation:

1. If the first diagnosis day/ month are missing and the year is non-missing:
 - a. If the year part of the first diagnosis date is equal to the year part of the inform consent date, then the imputed first diagnosis date is set to the year start point (01JanYYYY).
 - b. Otherwise the imputed first diagnosis date is set to the mid-year point (01JulYYYY).
2. If the first diagnosis day is missing and the month/year are non-missing:
 - a. If the month and year part of the first diagnosis date is equal to the month and year part of the inform consent date, then the imputed first diagnosis date is set to the month start point (01MONYYYY).
 - b. Otherwise the imputed first diagnosis date is set to the mid-month point (15MONYYYY).

5.2 AEs coding/grading

AEs are coded using the MedDRA terminology with the latest version at the analysis.

5.3 Laboratory parameters derivations

Not applicable

5.4 Statistical models

5.4.1 Analysis supporting primary objective(s)

5.4.1.1 Mixed model with repeated measures

For the primary efficacy endpoints (change from baseline in UAS7 or ISS7 or HSS7), a linear mixed model with repeated measures (MMRM) will be used to estimate treatment differences, based on the FAS. The MMRM model will include treatment group, the corresponding baseline score, actual randomization strata variables, week and both interaction of treatment by week and interaction of the corresponding baseline score by week as fixed effects. Repeated measures within subject are modeled using an unstructured covariance of the error terms.

The primary analysis will be performed based on the data after the missing data imputation for the intercurrent events have been performed. All data up to Week 12 will be included in the MMRM model for primary analysis.

The SAS procedure proc mixed will be used for this analysis with the following code:

```
ods output DIFFS=diff LSMeans=mean ConvergenceStatus=conv_mmrm1;
proc mixed data=..... covtest;
by _imputation_;
class subject group week region antige;
model change=baseline group week region antige group*week baseline*week/s
ddfm=kr cl;
repeated week/ type=UN subject=subject r;
lsmeans group*week /cl diff;
run;
```

where change = change from baseline UAS7 score

baseline = baseline UAS7 score

group = planned treatment group

(1 = LOU064 2 = Placebo)

week = study week

region = geographic region

antige = prior exposure to anti-IgE biologics

subject = subject

imputation = the index for imputation times

Note that the *mean* and *diff* datasets created will include all the treatment interactions for each week. The estimates for the right weeks, e.g. Week 12, and right treatment comparisons, e.g. LOU064 vs Placebo, should be subsetted by taking “week = **12** and _week=**12**” and “group= **1** and _group=**2**”.

If the computation of the MMRM model takes extreme amount of time, the ddfm=bw option could be considered. If the model with an unstructured covariance matrix does not converge, SAS will give a warning as “Unable to make hessian positive definite” or “Unable to Converge”. Meanwhile, the Status variable in the “convest” dataset created will take on the value 1 or 2. In this case, the compound-symmetry structure should be used.

Rubin’s Rule:

Rubin’s Rule will be applied to combine the multiple sets of estimates to produce the overall estimates, standard error, confidence interval and p-values.

The SAS procedure proc mianalyze will be used for this analysis with the following code:

```
proc mianalyze data=mean (where=(week=12)) ;
by group;
ModelEffects estimate;
stderr stderr;
ods output ParameterEstimates=est_mean;
run;

proc mianalyze data=diff (where=(week=12 & _week=12));
by group _group;
ModelEffects estimate;
stderr stderr;
ods output ParameterEstimates=est_diff;
run;
```

where *est_mean* includes the results for LS mean in each group, and *est_diff* includes the results for the treatment difference between groups.

If the datasets between imputations are identical after multiple imputation step, which will cause the SAS procedure proc mianalyze not runnable, the dataset with *_imputation_=1* will be used to create the results.

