2.2.1 Subgroup of interest

To explore the impact of disease characteristics at baseline on the efficacy, subgroup analysis will be provided on:

- UAS7 (for co-primary endpoints ISS7/HSS7) change from baseline over time
- Achievement of UAS7≤6 over time
- Achievement of UAS7=0 over time

The definition of subgroups are following,

- Duration of CSU defined as Time since diagnosis of urticaria, informed consent date – diagnosis date + 1 (≤1 year, >1 to 3 years, >3 to 5 years, >5 years)

Subgroup analyses will be performed for the primary endpoint and secondary endpoints using the randomization strata subgroups. If the actual stratum is different to the assigned stratum in IRT, the actual stratum will be used in the analysis.

Randomization strata

- Previous exposure to anti-IgE biologics (Yes/No)
- Geographic region (LaCAN (Latin America, Caribbean and Canada), RE (Region Europe), China, US, AMEA (Asia, Middle East & Africa))

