2.5.1.2 Statistical hypothesis, model, and method of analysis

The statistical hypothesis test for the primary endpoint being tested is that the absolute change from baseline in UAS7 score at Week 12 in remibrutinib is not superior to the placebo group i.e.:

$$H_{01}: \mu_{\text{remibrutinib}} \geq \mu_{\text{Placebo}} \text{ versus } H_{A1}: \mu_{\text{remibrutinib}} < \mu_{\text{Placebo}}$$

where μ is the mean change from baseline in UAS7 at Week 12.

A linear mixed model with repeated measures (MMRM) will be used to estimate treatment differences for change from baseline in UAS7 score at Week 12, based on the FAS. The MMRM model will include treatment group, baseline UAS7 score, randomization strata variables, week and both interaction of treatment by week and interaction of baseline UAS7 score by week as fixed effects. Repeated measures within participant are modeled using an unstructured covariance of the error terms. Additional important covariates may be added to the model. For the primary analysis, data up to Week 12 will be used in the model. The treatment difference LOU064 25 mg – placebo at Week 12 will be estimated using the LS mean and 95% CI, and p-value for treatment comparison will be presented.

The detailed testing strategy including the primary endpoint analysis is provided in [Section 2.5.2.1](#).

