5.4.3 Multiple imputations

Multiple imputation is a simulation-based approach where missing values are replaced by multiple Bayesian draws from the conditional distribution of missing data given the observed data and covariates, creating multiple completed data sets. These completed data sets can then be analyzed using standard methods. [Rubin \(1987\)](#) presented rules how to combine the multiple sets of estimates to produce overall estimates and confidence intervals that adequately incorporate missing data uncertainty. The multiple imputation analysis will be imputed based on the individual treatment arm information.

Missing values for UAS7/HSS7/ISS7/AAS7/DLQI will be imputed separately. The imputation is done on the original post-baseline score and the imputation model will include treatment group, the corresponding baseline score, actual randomization strata variables, week and both interaction of treatment by week and interaction of the corresponding baseline score by week. The number of imputations is 100. The imputed values may exceed possible range of variables. In this case, the imputed values which exceed possible maximum value (e.g., 42 for UAS7) will be replaced with the maximum value, the imputed values which exceed possible minimum value (e.g., 0 for UAS7) will be replaced with the minimum value.

Multiple imputation will be implemented using the RMConjPlus20 and RefBTBV04 SAS macro. The macros are available from the website of London school of Hygiene & tropical

medicine (LSHTM) on <https://www.lshtm.ac.uk/research/centres-projects-groups/missing-data#dia-missing-data>. The purpose and activities of each of the two macros is described below. For more details of these two macros please see “The RMConjPlus and RefbTbV SAS macros” by James H. Roger (2023) at <https://www.lshtm.ac.uk/research/centres-projects-groups/missing-data#dia-missing-data>.

The %RefBTBV SAS macro is used to set up the design matrix for reference-based imputation. This macro creates an input data set for %RMConjPlus by generating the required Treatment*Visit part of the design matrix based on the chosen reference-based imputation method (J2R, CIR, CR, etc.).

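### The only fallback for a non-converging primary MMRM is compound symmetry, which would understate the Week 12 standard error if the SD of change rises over time: unlikely to be triggered, cheap to replace

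*SAP*

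**What the plan says.** Protocol 12.4.2 and SAP 2.5.1.2 specify the covariance structure for the primary model: "Repeated measures within participant are modeled using an unstructured covariance of the error terms". The code in SAP 5.4.1.1 agrees: "repeated week/ type=UN subject=subject r". Every weekly score enters the model ("All data up to Week 12 will be included in the MMRM model for primary analysis"), and the weekly eDiary windows in SAP 2.1.1.5 make that 12 visits.

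The model is fitted to completed data: "The primary analysis will be performed based on the data after the missing data imputation for the intercurrent events have been performed". SAP 5.4.3 sets the number of datasets ("The number of imputations is 100"). The code runs once per imputed dataset, and Rubin's rules combine the results.

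The protocol names no fallback. SAP 5.4.1.1 adds one. It begins "If the model with an unstructured covariance matrix does not converge, SAS will give a warning" and ends "In this case, the compound-symmetry structure should be used". No heterogeneous structure is listed and the code has no sandwich variance option. The only other option offered is a different degrees-of-freedom method if computing time is excessive.

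Two details are unsettled. The SAP does not say whether one failed dataset switches one fit or all 100. The text also looks for the convergence status in a dataset called convest, while the code writes it to conv_mmrm1.

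**The concern.** Compound symmetry in its ordinary sense has one variance for all visits and one covariance for all pairs of visits. With all 12 weeks in the model, the standard error of the Week 12 difference would come from the average of the 12 weekly variances. If the spread of change from baseline is larger at Week 12 than earlier, that average is too small for the visit being tested. Neither Kenward-Roger nor between-within degrees of freedom repairs a wrong variance structure.

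At stake are the width of the reported confidence intervals and the one-sided 0.025 level for change in UAS7, ISS7 and HSS7, since SAP 5.4.1.1 applies the same model to all three. A fallback matters only when the planned model has failed, so it should hold the stated error rate in that case. The missing rule for partial failure would leave a choice to be made after the results are known.

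**Working it through.** **Inputs from the documents** (SAP 3.1, the same in protocol 12.8.1): UAS7 difference 10, SD 12 at Week 12, one-sided alpha 0.025, 300/150 randomized, 270/135 after 10% drop-out. For ISS7 and HSS7 the difference is 4 and the SD 6. **Assumed:** the SD at Weeks 1 to 11, because no week-by-week SDs are given.

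**1. The plan's own figure.** SE = 12 × sqrt(1/270 + 1/135) = 1.265, and 10/1.265 = 7.91. Power from the noncentral t distribution is above 0.99999 for UAS7 and 0.99999 for ISS7 or HSS7. The stated figure of more than 99% reproduces.

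**2. Standard error under each structure.** With complete data and N = 300/150:
- Unstructured: SE = 12 × sqrt(1/300 + 1/150) = 12 × 0.1 = 1.200.
- Compound symmetry: SE = sqrt(mean of the 12 weekly variances) × 0.1.
- Ratio r = SE(compound symmetry)/SE(unstructured). True one-sided alpha = 1 − Φ(1.96 × r), and coverage of the 95% interval = 2Φ(1.96 × r) − 1.

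Example, linear rise from 8 to 12: the 12 SDs have mean 10, and their variance is (4/11)² × 143/12 = 1.576. The mean weekly variance is 100 + 1.576 = 101.58, its root is 10.08, and r = 10.08/12 = 0.840.

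**3. Results if all 100 fits switch.**

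| Assumed SD of change | SE | r | One-sided alpha | Coverage |
|---|---|---|---|---|
| Constant 12 | 1.200 | 1.000 | 0.025 | 95.0% |
| 10, reaching 12 by Week 4 | 1.168 | 0.974 | 0.028 | 94.4% |
| 8, reaching 12 by Week 4 | 1.141 | 0.950 | 0.031 | 93.8% |
| Linear, 10 to 12 | 1.102 | 0.918 | 0.036 | 92.8% |
| Linear, 8 to 12 | 1.008 | 0.840 | 0.050 | 90.0% |
| Linear, 14 down to 12 | 1.302 | 1.085 | 0.017 | above 95% |

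**4. Simulation.** There were 15,000 null trials per case at 300/150 over 12 weeks, with the baseline score as covariate. For 8 to 12, the empirical SD of the Week 12 estimate was 1.197. The mean SE was 1.200 unstructured and 1.008 under compound symmetry, and type I error was 0.0235 and 0.0493. For 10 to 12, type I error was 0.0230 and 0.0329. With constant SD it was 0.0257 and 0.0245. A single REML fit with the SAP's fixed effects (8 to 12) gave SE 1.045 under compound symmetry, against 1.250 from a Week 12 ANCOVA.

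**5. If only some fits switch.** Rubin's rules average the within-imputation variances. With a fraction f switched, alpha = 1 − Φ(1.96 × sqrt(1 − f(1 − r²))). For the 8-to-12 case r² = 0.706:
- 1 of 100: 0.0252
- 5 of 100: 0.0259
- 10 of 100: sqrt(1 − 0.1 × 0.294) = 0.985, alpha 0.0267

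Steps 3 and 5 leave out the between-imputation variance, which would dilute the bias slightly.

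**The case against.** The strongest reply is that the trigger is remote. An unstructured matrix over 12 weeks has 12 × 13/2 = 78 parameters, against about 450 participants with no gaps after imputation. The imputation step in SAP 5.4.3 already assumes unstructured covariance, so data that could not support one would probably show it there first. The 100 datasets are not 100 independent chances of failure, because they share all the observed values. This stands.

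Next, rising variance is not documented. Protocol 4.2 and 4.5 describe fast onset, which fits an early plateau better than a steady 12-week rise. In the other direction, the composite rule in SAP 2.5.1.3 sets UAS7 to 42 after cyclosporin or systemic corticosteroid use, and counts that use only after Week 8, which could widen the late spread. The documents do not give its expected frequency. The pattern is therefore open, and only a range can be given.

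Finally, the code reports convergence separately for each dataset, so switching fit by fit is a natural reading, and step 5 shows that a few switches hardly matter. At the planned effect the test statistic is about 8, so a 16% error in the SE would not change the decision. Both stand.

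What survives is narrower. The SAP states a definite rule which, if used across the imputations, is right only when the variance is about constant.

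**Conclusion.** The point holds as a conditional weakness of low priority. If the unstructured model failed in all 100 datasets and the SD of UAS7 change rose to 12 at Week 12, one-sided alpha would be about 0.028 to 0.031 with an early plateau, and 0.036 or 0.050 with a linear rise from 10 or 8. Under constant SD there is no bias, and under falling SD the test is conservative.

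A reader might infer that the primary test as planned runs at up to twice its nominal level. The documents do not support that: the planned model is unstructured, and the upper figure needs it to fail in every imputation and the SD to keep rising to Week 12.

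A reader might also take the subgroup analyses in SAP 2.2.1 ("UAS7 (for co-primary endpoints ISS7/HSS7) change from baseline over time") as a second route to type I error inflation. Non-convergence is more likely in small groups, but these analyses lie outside the alpha-controlled hierarchy and that section names no model for them.

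The exposed tests differ by scenario. With ISS7 and HSS7 as co-primary endpoints, they are those two and the first-ranked secondary, UAS7 change. With UAS7 as primary, they are the primary and the ISS7 and HSS7 secondaries; the two secondaries ranked first there are responder endpoints analysed by logistic regression.

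**What to change.** Replace the compound-symmetry sentence in SAP 5.4.1.1 with:

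> If UN fails to converge in any imputed dataset, use in all 100 datasets the first structure that converges in all of them from heterogeneous Toeplitz, heterogeneous AR(1), heterogeneous CS; if none does, use a Week 12 ANCOVA with the same covariates in each imputed dataset, combined by Rubin's rules.

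This lets Week 12 keep its own variance and settles partial failure. The ANCOVA is available because the data are complete after imputation, and it needs no covariance structure. A sandwich variance is the less tidy choice here, because it would also need a replacement for the Kenward-Roger degrees of freedom in the code.

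Make the convergence dataset named in the text match the code (conv_mmrm1). If the primary analysis has already been run, state whether any fit used compound symmetry and, if so, rerun it under the new rule.

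The cost is one sentence, a few lines of code, and possibly slightly wider confidence intervals when the fallback is used.
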